7. EFFICACY EVALUATION

7.1 Analysis of Primary Efficacy Outcome Measure

All derivations, analyses and summaries are not applicable (details in Section 1 and Section 5.3).

The primary outcome measure is the GvHD overall response rate, the proportion of subjects achieving overall response at Day 28. The overall response is defined as GvHD CR + PR, which are defined as follows:

- GvHD CR is complete resolution of all signs and symptoms of acute GvHD in all organs without intervening salvage
- GvHD PR is improvement of 1 stage in 1 or more organs involved in GvHD without progression in other organs

Overall response at Day 28 will be based on the response assessments at Day 28 with a +1- day window for this assessment. For the primary analysis in the efficacy analysis set, the NRI approach will be used to impute the missing response assessment at Day 28. For the GvHD overall response rate at Day 28 95% exact confidence intervals of the proportion will be calculated with Clopper-Pearson method.

The primary analysis of the GvHD overall response rate in the efficacy analysis set will use the investigators' response assessment collected on the CRF Investigator Response Assessment [INVRES] module and use NRI approach for missing response assessment.

A sensitivity analysis in the efficacy analysis set will use the adjudicated response assessments by an adjudication committee and use NRI approach for missing response assessment.

All the planned analyses of the GvHD overall response rate at Day 28 are listed in the table below.

Analysis	Analysis set	Response assessment data	Approach for missing response assessment imputation
Primary analysis	Efficacy analysis set	Investigators' assessment	NRI
Sensitivity analysis	Efficacy analysis set	Adjudicated data	NRI

Response assessments for each subject will be listed by visit.

7.2 Analysis of Secondary Efficacy Outcome Measure

All derivations, analyses and summaries are not applicable (details in Section 1 and Section 5.3).

7.2.1 Key Secondary Efficacy Outcome Measures

The key secondary efficacy outcome is the GI response rate, the proportion of subjects achieving GI response at Day 28. GI response is defined as GI CR + PR, which are defined as follows:

- GI CR is defined as
 - a) Able to eat; not requiring parenteral nutrition, and
 - b) Passing primarily formed stools
- GI PR is defined as
 - a) Decrease in need for parenteral nutrition to $\leq 50\%$ of required calories; and
 - b) Reduction of stool volume by $\geq 50\%$, without ileus

GI response at Day 28 based on investigator assessments (CRF INVRES module) and adjudicated data will be analyzed using the same approach as described for the primary outcome in Section 7.1.

7.2.2 Other Secondary Efficacy Outcome Measures

Proportion of subjects achieving GvHD overall response at Day 56

GvHD overall response at Day 56 will be based on all the investigators' assessments or the adjudicated data of GvHD response obtained at Day 56 (with a +1 day window) in the efficacy analysis set and using the NRI approach as for the primary outcome measure in Section 7.1.

Change from baseline in acute GvHD grading at Days 28, 56 and 180

Staging of GvHD will be performed by the investigator according to the modified IBMTR grading system, and recorded on CRF STAGE module. The degree of involvement of skin, GI and liver is classified by stage on a scale of 0 to 4 and the grade of acute GvHD is classified on a scale of A to D.

Shift tables from baseline to Days 28, 56 and 180 visits will be provided for acute GvHD grading and organ system (involvement of skin, GI and liver) staging separately in the efficacy analysis set.

Incidence of chronic GvHD at Days 100, 180 and 365

At baseline and Days 100, 180 and 365, the investigator will assess the subject for chronic GvHD and acute/chronic GvHD overlap syndrome. The number and percentage of subjects who have clinical evidence of chronic GvHD will be summarized at baseline and Days 100, 180 and 365 by organ systems (skin involvement, dry mouth/mouth sores/ulcers, dry eyes, joint involvement, liver involvement with cholestasis, esophageal involvement, obstructive lung disease) in the SAF.

Duration of any overall response

Duration of overall response is defined as the time from the date of first overall response (GvHD CR or PR) until the first date of progression (GvHD progressive disease [PD] on CRF INVRES module) or death in the absence of progression. Subjects without progression or death will be censored at the date of last GvHD response assessment.

Only subjects with an overall response will be summarized for duration of overall response. Descriptive data, including 25th percentile, median and 75th percentile will be estimated using Kaplan-Meier method. The summaries will be produced separately for investigator assessment and adjudicated data. Duration of overall response will also be presented using corresponding Kaplan-Meier plots.

Duration of any GI response

Duration of GI response will be derived and summarized for subjects who achieved a GI response using the same approach as described for the duration of overall response above, based on GI response assessments.

Overall survival through Days 100, 180 and 365

Overall survival is defined as the time from the date of first dose of study treatment until death (CRF DEATH module) due to any cause in the SAF. Any subject not known to have died in Part 1 will be censored at the date of study completion/early termination (or the last recorded date during the study).

Number and percentage of subjects who have died will be provided along with median overall survival time. Overall survival through Days 100, 180 and 365 will be presented as the Kaplan-Meier estimates of the probability of subjects' being alive at Days 100, 180 and 365. The probability of overall survival will be presented in a Kaplan-Meier plot.

All-cause, transplant-related, infection-related and GvHD-related mortality at Days 28, 56, 100 and 180

All-cause, transplant-related, infection-related and GvHD-related mortality will be collected with the cause of death based on the investigator's assessment. These categories are not mutually exclusive and they are defined as:

- Transplant-related mortality: death related to transplantation (including deaths related to GvHD)
- Infection-related mortality: death related to infection (including infections related to HSCT)
- GvHD-related mortality: death related to GvHD
- Other cause: any death not related to transplant, infection or GvHD

The proportion of subjects with all-cause mortality is a reverse of the proportion of subjects alive (overall survival). The mortalities at Days 28, 56, 100 and 180 and 95% confidence intervals will be estimated using the uncorrected Kaplan-Meier method. The cumulative mortality rate will be presented in a Kaplan-Meier plot.

Time to transplant-related, infection-related and GvHD related mortality are potentially dependent and competing mortality causes for a subject, and will be analyzed using the competing risk approach. These outcomes will be defined as the time from the date of

first dose of study treatment until death due to the corresponding cause, in the presence of other mortality causes. Any subject not having death will be censored at the date of study completion/early termination (or the last recorded date during the study). For time to transplant-related mortality, subjects having death due to a reason other than transplant-related will be censored at the date of death, and handled differently in the estimation from the censoring not due to a competing cause. Time to infection-related mortality and time to GvHD-related mortality will be censored for subjects without an event in a similar fashion. The probability of transplant-related, infection-related and GvHD-related mortality at Days 28, 56, 100 and 180 will be estimated using the competing risk estimate of cumulative incidence function. GvHD-related mortality will also be presented using a cumulative incidence rate plot.

Failure-free survival at Days 100 and 180

Failure-free survival is defined as the time from the first dose date of study treatment until death or the first date of failure-free survival not achieved (CRF Mortality and Survival Assessments [MORTAL] module), whichever comes earlier. The failure-free survival are determined by investigator with the absence of all 3 of the following criteria:

- Need for second-line treatment for acute GvHD. Second-line treatment is defined as any additional systemic treatment used for steroid nonresponsive treatment of acute GvHD. Methylprednisolone (or equivalent steroid) doses greater than 2 mg/kg required for the treatment of GvHD will also be considered second-line therapy
- Non-relapse mortality. Non-relapse mortality is defined as death during continuous complete remission
- Recurrent malignancy

Subjects without recorded death and failure-free survival not achieved at any survival and mortality assessment will be censored at the date of last mortality and survival assessment.

Failure-free survival will be summarized at Days 100 and 180 using the same approach (Kaplan-Meier) as described for overall survival.

GvHD-free survival at Days 28, 56, 100 and 180

GvHD-free survival is defined as the time from the first dose date of study treatment until death or the first date of GvHD-free survival not achieved (CRF MORTAL module), whichever comes earlier. Subjects without recorded death and GvHD-free survival not

achieved will be censored at the date of last mortality and survival assessment. GvHD-free survival will be summarized at Days 28, 56, 100 and 180 using the same approach (Kaplan-Meier) as described for overall survival.

8. SAFETY EVALUATION

8.1 Extent of Exposure

All derivations, analyses and summaries are not applicable (details in Section 1 and Section 5.3).

The below summaries related to study treatment will be produced for the SAF set:

- Duration of exposure of study treatment (days): date of last dose – date of first dose + 1
- Number of infusions received
- Number of subjects and reason for infusion rate change
- Number of subjects and reason for infusion interruption

8.2 Adverse Events

All derivations, analyses and summaries are not applicable (details in Section 1 and Section 5.3).

Adverse events (AEs) will be collected throughout the study, from the time the informed consent is signed until study completion. All AEs will be coded using MedDRA, version 19.1 or a later version, and graded according to National Cancer Institute (NCI) Common Terminology Criteria for Adverse Events (CTCAE) Grade (version 4.03).

A treatment-emergent AE (TEAE) is defined as an AE that occurred during or after study treatment application and until 30 days following the last dose of the study treatment. If the start date and time of the AE is provided, then the AE start date and time will be used to classify the AE as TEAE or not. If the start date and time or start time of an AE is unavailable, the CRF AE module asks the subject/investigator to identify whether it occurred before the first treatment, during treatment, within 24 hours after the last treatment, between 24 and 72 hours after last treatment, or more than 72 hours after the last treatment. This information will be used to determine if the AE will be considered as TEAE, when necessary.

The number and percentage of subjects reporting the following TEAEs will be tabulated by SOC, PT and severity CTCAE grade, for the SAF set:

- All TEAEs
- TEAEs related to study treatment
- TEAEs with CTCAE grade 3 or 4
- TEAEs with CTCAE grade 3 or 4, related to study treatment
- Serious TEAEs
- Serious TEAEs related to study treatment
- TEAEs leading to discontinuation of study treatment
- Temporally-associated TEAEs (occurring within 72 hours of termination of infusion)

An overall summary of the number and percentage of subjects in each category will be presented. Overview summaries of TEAEs by seriousness, severity CTCAE grade and relationship to study treatment (categories as collected and dichotomized) will be provided, separately as the subject-level and event-level summaries. Additionally, subjects with non-serious TEAEs will be presented by SOC, PT, severity CTCAE grade and dichotomized relationship to study treatment.

The following conventions will be followed in summarizing TEAEs:

- For subject incidence summaries, each subject will be counted only once within each system organ class and within each preferred term.
- If a subject reports more than one TEAE within a preferred term and/or a body system, the TEAE with the highest known CTCAE grade within each body system and within each preferred term will be included in the summaries by CTCAE grade.
- For summaries related to study treatment, AEs whose relationship to treatment are assessed as “possibly related”, “probably related” or missing will be included.

Listings of AEs that occurred before treatment application, non-serious AEs that occurred during or after treatment application, serious AEs that occurred during or after treatment application, all deaths, and AEs leading to study treatment discontinuation will be produced, including all data collected in the CRF, along with derived duration of AEs,

calculated as (end date – start date +1). If an event is ongoing at the end of the study then the duration of the event will not be calculated.

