6.4.2 Clinical Studies

GLASSIA has been evaluated in 2 clinical studies in adult subjects with A₁PI deficiency, 1 clinical study in subjects aged 9 to 18 years with type 1 diabetes mellitus and 1 Phase 4 clinical study in healthy adult subjects. GLASSIA was generally safe and well tolerated in all studies; the majority of adverse events (AEs) reported were of mild or moderate severity. All serious adverse events (SAEs) reported in the clinical studies were assessed by the investigator as unrelated to GLASSIA. Three treatment-emergent SAEs were reported in the studies: cholangitis, exacerbation of chronic obstructive pulmonary disease and pulmonary emboli. All 3 SAEs were reported in the Phase 2/3 study of adult subjects with A₁PI deficiency.

One subject in the Phase 2/3 study experienced a treatment-emergent serious adverse reaction (infective exacerbation of chronic obstructive pulmonary disease), considered possibly related to GLASSIA due to its temporal association.

One ongoing Phase 1/2 study is being conducted in subjects with steroid-refractory acute GvHD (Study FHCRC 2571). An interim analysis was conducted with the 12 subjects in Cohorts 1 and 2 in Study FHCRC 2571. Cohort 1 received a loading dose of GLASSIA of 90 mg/kg IV on Day 1, followed by 30 mg/kg every other day through Day 15. Cohort 2 received a loading dose of GLASSIA of 90 mg/kg IV on Day 1, followed by 60 mg/kg every other day through Day 15. In the interim analysis, most AEs were of mild or moderate severity. Two subjects experienced bowel perforation 3 weeks and 2 months, respectively, after the last dose of GLASSIA. Neither AE resulted in death. Both AEs were assessed by the investigator as possibly related to GLASSIA; the study's Data Safety Monitoring Board reviewed the events and concluded that the 2 bowel perforation events were not related to GLASSIA, but instead were related to viral infections. One fatal SAE in the study was assessed as possibly related to GLASSIA: liver failure, which occurred <30 days after the last dose of GLASSIA. Most AEs during the study were consistent with those expected in subjects undergoing HSCT or experiencing GvHD and do not preclude further investigation of GLASSIA in GvHD.

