9.3 Withdrawal from Study Participation and Discontinuation of Study Treatment

Any subject may voluntarily withdraw at any time consent for continued participation in the study and data collection. Every effort should be made prior to enrollment to ensure subjects are willing to comply with study procedures and assessments. The reason for withdrawal will be recorded on the End of Study CRF. Additionally, the investigator and sponsor have the discretion to discontinue any subject from the study if, in their judgment, continued participation would pose an unacceptable risk for the subject. Assessments to be performed at the termination visit (including in cases of withdraw or discontinuation) are described in Section 10.6 and Section 20.2.

Whenever possible, all subjects who prematurely withdraw from the study will be followed through Day 28 or 2 weeks after the last dose of study treatment, whichever comes later (refer to Section 10.6 for additional details), unless otherwise indicated below.

Subjects will be discontinued from study treatment for the following reasons:

- The subject has a lower GI biopsy within 7 days of informed consent that in the opinion of a pathologist is inconsistent with acute GvHD (Section 11.3). If the results are obtained prior to the first dose of study treatment, the subject will be withdrawn from the study prior to study treatment for Part 1 and without being randomized for Part 2.
- The subject becomes pregnant.
- The subject starts a second-line treatment for acute GvHD prior to Day 28 (Section 8.2).
- The subject experiences recurrent malignancy (Section 12.11).
- If the Sponsor medical monitor or the investigator deem it is in the best interest of the subject

Subjects who discontinue study treatment and/or the study will not be replaced.

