10.6 Subject Completion/Discontinuation

A subject is considered to have completed the study when he/she ceases active participation in the study according with the protocol (with or without protocol deviations).

Reasons for completion/discontinuation will be reported on the Completion/Discontinuation CRF, including: completed, screen failure, AE (eg, death), discontinuation by subject (eg, lost to follow-up [defined as 3 documented unsuccessful attempts to contact the subject], dropout), physician decision (eg, pregnancy, progressive disease, non-compliance with IP/protocol violation(s), recovery), study terminated by sponsor, or other (reason to be specified by the investigator, eg, technical problems). Regardless of the reason, all data available for the subject up to the time of completion/discontinuation through the study follow-up period should be recorded on the appropriate CRF.

Every effort will be made to have discontinued subjects complete the study completion/termination visit. If the study completion/termination visit is done as an additional, unscheduled visit, the assessment results shall be recorded with the study completion/termination visit. If a subject terminates participation in the study and does not return for the study completion/termination visit, their last recorded assessments shall remain recorded with their last visit. The reason for discontinuation will be recorded, and the data collected up to the time of discontinuation will be used in the analysis and included in the clinical study report. If additional assessments are required, the assessments shall be recorded separately. Assessments to be performed at the study completion/termination visit (including in cases of withdraw or discontinuation) can be found in Supplement 20.2 Schedule of Study Procedures and Assessments.

Subjects who discontinue study treatment prior to Day 28 will complete the Day 28 visit on Day 28 (± 1 day). If at least 2 weeks have passed since the last dose of study treatment, the Day 28 visit will serve as the study completion/termination visit. If Day 28 is less than 2 weeks following the last dose of study treatment, subjects will complete the Day 28 visit and then the study completion/termination visit 2 weeks (± 1 day) after the last dose of study treatment. In this event, the study completion/termination visit will consist of an office visit with the same assessments as the Day 365 visit.

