Subjects who discontinue study treatment after Day 28 will complete the study completion/termination visit as an office visit 2 weeks (± 1 day) after the last dose of study treatment. Subjects who withdraw from the study after Day 56 will be encouraged to complete the study completion/termination visit at the time of discontinuation. In the event that it is not feasible for the subject to visit the site at the study completion/termination visit after Day 56, the visit may be conducted with a phone call.

Subjects who discontinue study treatment will not attend any other subsequent visits other than Day 28 and the study completion/termination visit (if applicable), except as needed for follow-up of recovering/resolving AEs (see Section 12.1.2).

In the event of subject discontinuation due to an AE, clinical and/or laboratory investigations that are beyond the scope of the required study observations/assessments may be performed as part of the evaluation of the event. These investigations will take place under the direction of the investigator in consultation with the sponsor, and the details of the outcome may be reported to the appropriate regulatory authorities by the sponsor.

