12.1.2 Assessment of Adverse Events

For the purposes of this study, changes in the severity or duration of GvHD experienced after the first IP exposure are collected as an efficacy endpoint and thus are not reportable on the AE CRF, nor will they be included in the analysis of AEs.

Symptoms or diagnostic findings of GvHD, such as skin rashes, abnormal liver function tests, diarrhea, ileus and bowel perforation, should be collected on the AE CRF only if there is an increase in the severity, duration or frequency AND if they begin after first exposure to IP.

All other AEs from the first IP exposure until study completion will be described on the AE CRF using the medical diagnosis (preferred), or, if no diagnosis could be established at the time of reporting the AE, a symptom or sign, in standard medical terminology in order to avoid the use of vague, ambiguous, or colloquial expressions (see definition in Section 12.1). Each AE will be evaluated by the investigator for:

- Seriousness as defined in Section 12.1.1.1
- Severity as defined in Section 12.1.2.1
- Causal relationship to IP exposure or study procedure as defined in Section 12.1.2.2

For each AE, the outcome (ie, recovering/resolving, recovered/resolved, recovered/resolved with sequelae, not recovered/not resolved, fatal, unknown) and if applicable action taken (ie, dose increased, dose not changed, dose reduced, drug interrupted, drug withdrawn, not applicable or unknown) will also be recorded on the AE CRF. Recovering/resolving AEs will be followed until resolution or 30 days after the study completion/termination visit, whichever comes first. The follow-up information will be documented in the AE CRF. If the severity rating for an ongoing AE changes before the event resolves, the original AE report will be revised (ie, the event will not be reported as separate AE). During the course of any AE, the highest severity rating will be reported.

Deviations from protocol-specified procedures of IMP use such as overdosing, underdosing, withdrawal, omission, incorrect route of administration, and use of a product other than the IMP, standard care of the underlying disease or treatment of a TEAE shall be recorded in the Protocol Deviation Form.

Any pregnancy that occurs after administration of IP will be reported on a Pregnancy Report Form.

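### TEAEs are counted to 30 days after the last dose, but under protocol 10.6 subjects who stop early are observed for only 14 to 28 of those days, and the follow-up rules contradict each other

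*SAP*

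**What the plan says.** **Counting window.** In SAP 8.2 a treatment-emergent AE "is defined as an AE that occurred during or after study treatment application and until 30 days following the last dose" of study treatment.

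**Collection period.** The same section collects AEs "from the time the informed consent is signed until study completion". Protocol 12.1.2 agrees: "All other AEs from the first IP exposure until study completion will be described on the AE CRF". After the termination visit, 12.1.2 provides only for following AEs that are already recovering or resolving, for up to 30 days. It does not provide for seeking new ones.

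**When an early stopper completes.** Protocol 9.3 says that subjects who withdraw prematurely "will be followed through Day 28 or 2 weeks after the last dose of study treatment, whichever comes later", whenever possible. Protocol 10.6 gives the detail:
- Stopping before Day 28, with at least 2 weeks since the last dose: "the Day 28 visit will serve as the study completion/termination visit".
- Stopping before Day 28, with less than 2 weeks since the last dose: the Day 28 visit, then a termination visit 2 weeks after that dose.
- Stopping after Day 28: the termination visit takes place "as an office visit 2 weeks (± 1 day) after the last dose of study treatment".

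These subjects attend nothing further except for unresolved AEs. The schedule footnotes in protocol 20.2 and SAP 14.2 repeat this.

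**The opposing rule.** Protocol 8.2, under Treatment Failures, and SAP 2 both state that all subjects are followed at Days 100, 180 and 365.

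**Denominator.** Under SAP 4.2 and 5, percentages are taken over everyone who received at least one dose.

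**The concern.** A TEAE percentage assumes that each subject in the denominator was watched for the whole window in which an event would count. If 10.6 governs, that is true of subjects who finish dosing and untrue of every early stopper.

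The shortfall is not random. Second-line therapy before Day 28 and recurrent malignancy both force discontinuation, so observation is shortest in subjects who are doing badly.

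Late events are plausible in this setting. Protocol 6.4.2 reports from the earlier GvHD study: "Two subjects experienced bowel perforation 3 weeks and 2 months, respectively, after the last dose of GLASSIA". The first of these falls inside a 30-day window but, for many stopping days, after the last planned visit.

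**Working it through.** The documents give no AE rate or expected count here, so there is no planned figure to reproduce. The check compares the planned observation period with the counting window.

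**Inputs.** Window: last dose + 30 days (SAP 8.2). End of observation for an early stopper: the later of Day 28 and last dose + 14 (protocol 9.3 and 10.6). Dosing days before the final one: 0, 2, 4, 6, 8, 10, 12, 14, 21, 28, 35 and 42 (protocol Table 1). Visit windows of ±1 day are ignored.

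**Formulas**, with d the day of the last dose:
- post-dose days observed = max(28 − d, 14)
- share of the 30 days not observed = 1 − observed/30
- share of the whole TEAE window observed = max(28, d + 14)/(d + 30)

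| Last dose, d | Post-dose days observed | Not observed, of 30 | Whole window observed |
|---|---|---|---|
| 0 | 28 | 7% | 28/30 = 93% |
| 2 | 26 | 13% | 28/32 = 88% |
| 4 | 24 | 20% | 28/34 = 82% |
| 6 | 22 | 27% | 28/36 = 78% |
| 8 | 20 | 33% | 28/38 = 74% |
| 10 | 18 | 40% | 28/40 = 70% |
| 12 | 16 | 47% | 28/42 = 67% |
| 14 | 14 | 53% | 28/44 = 64% |
| 21 | 14 | 53% | 35/51 = 69% |
| 28 | 14 | 53% | 42/58 = 72% |
| 35 | 14 | 53% | 49/65 = 75% |
| 42 | 14 | 53% | 56/72 = 78% |

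All 12 early-stop days fall short of 30; five sit at the 14-day floor. The SAP keeps the original calendar (first dose on Day 1), which gives 27, 25, 23, 21, 19, 17 and 15 days for last doses on Days 1 to 13, and 14 from Day 15 on. The pattern is the same.

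**Completers.** Last dose Day 49; 49 + 30 = Day 79, before the Day 100 visit. Covered.

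**An event 21 days after the last dose.** It is within planned observation when 28 − d ≥ 21, that is d ≤ 7: last doses on Days 0 to 6, 4 of the 12 days. For Day 8 or later (8 of 12) it counts as treatment-emergent but no planned visit would look for it.

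**Effect on risk, under an assumed constant hazard.** If R is the true 30-day post-dose risk, the risk seen in k days is 1 − (1 − R)^(k/30).

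| True R | k = 14 | k = 22 | k = 28 |
|---|---|---|---|
| 5% | 2.4% | 3.7% | 4.7% |
| 10% | 4.8% | 7.4% | 9.4% |
| 20% | 9.9% | 15.1% | 18.8% |

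These are risks among early stoppers. In the full safety set the loss is diluted. Take R = 10% for everyone and suppose a fraction f stop early with 14 days observed. The crude figure is then 10% − f × (10% − 4.8%): 9.5% for f = 10%, 8.4% for f = 30% and 7.4% for f = 50%. The documents do not give f, so these values are assumptions.

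**If protocol 8.2 governs instead.** The latest early stop gives 42 + 30 = Day 72, before Day 100, so every window is covered.

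**The case against.** **The gap depends on which rule applies.** This is the strongest point against, and it stands. If the all-subject follow-up in protocol 8.2 and SAP 2 governs, there is no shortfall. But 10.6 is the more specific text, the schedule footnotes of both documents repeat it, and the general design text in protocol 8.2 promises withdrawn subjects only follow-up to at least Day 28, with a reference to 10.6. The documents contradict themselves, and the reader cannot tell which rule a site would follow.

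**A reader might infer that early stoppers get only 14 days.** That is the floor, reached for a last dose on Day 14 or later. The earliest stop for no change in GvHD status is about Day 6, which leaves 22 days.

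**A reader might infer that a perforation at 3 weeks would go unseen.** The documents do not support that. For last doses up to Day 6 it falls within planned observation. For later stops it would not be actively sought, but protocol 2 requires SAEs to be sent to the sponsor within 24 hours of awareness, so a site that learned of it could still report it. Non-serious events lack that expedited route. Protocol 6.4.2 adds that the earlier study's safety board judged both perforations unrelated to GLASSIA, although the investigator had called them possibly related. The one at 2 months lies outside any 30-day window.

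**A reader might infer a bias between the Part 2 arms.** The 30-day definition appears only in the Part 1 SAP. No Part 2 SAP was written, and the protocol's safety analysis sets no such window. Between-arm bias would arise only if the definition were carried over and the arms differed in early stopping.

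**Crude AE percentages are conventional.** That is true, but SAP 8.5 and 8.6 already censor at last follow-up for malignancy and infection, so the same treatment of TEAEs is not foreign to this plan.

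**Conclusion.** The mismatch holds, conditionally. If 10.6 governs, every early stopper is observed for 14 to 28 of the 30 post-dose days, a shortfall of 2 to 16 days, while completers have none. Crude TEAE percentages would then be biased low for early stoppers. At a constant event rate their event counts over the whole TEAE window would be 7% to 36% low, depending on the stopping day. Subject-level percentages, which count each subject once per term, would lose proportionally less. The constant rate is an assumption that the documents neither support nor exclude.

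Whatever the size, protocol 8.2 and SAP 2 contradict protocol 10.6 and SAP 14.2 on follow-up after stopping, and that needs settling on its own account.

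It would be wrong to read this as an error in a reported result. SAP 8.2 is marked not applicable, one subject was enrolled, and only listings will be produced. The point concerns the prespecified design and any reuse of it.

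**What to change.** 1. **Reconcile the follow-up rules.** Protocol 8.2 and SAP 2 should agree with protocol 9.3 and 10.6 and with the schedule footnotes in both documents, so that AE ascertainment for early stoppers runs to at least 30 days after the last dose. One way is to add to 10.6 an AE and SAE contact at that time. This needs new text, because 10.6 mentions a telephone visit only for a termination visit after Day 56.
2. **Handle missing contacts in the analysis.** Where the contact is not made, end time at risk at last contact. Report TEAEs per subject-time observed, or as cumulative incidence, beside the crude percentage. SAP 8.5 and 8.6 already do the latter for malignancy and infection.

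The cost is one contact per early stopper and one extra column in the AE tables. With the contact made, coverage becomes 30 of 30 days for every stopping day. For the terminated study nothing needs to be re-run.
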